### **5.3. Methods to Manage Missing Data**

#### **5.3.1. Immunogenicity Data**

As assay data are expected to be missing completely at random, the primary analysis for the primary objectives will be based upon the observed, determinate observations. No imputation will be performed. The proportion of subjects with missing immunogenicity data may be summarized at each blood sampling visit for each primary MenB strain. The denominator will be the ITT population (all randomized). The category of missing reasons (quantity not sufficient [QNS], indeterminate, not done, dropout) may also be summarized. Similar summaries may also be performed to evaluate the proportion of missing hSBA-MenA, hSBA-MenC, hSBA-MenW, and hSBA-MenY titers.

If 10% or more of the subjects in any strata have missing hSBA data for the 4 primary MenB strains, a sensitivity analysis using mixed-effects model with repeated measures (MMRM) for Groups 2 and 4 will be applied for the primary MenB strains (GMT). The MMRM uses maximum likelihood estimation under the assumption that the missingness is at random (MAR). To account for the intrasubject correlation among the repeated measures, an unstructured covariance matrix will be used. In case the model does not converge, further covariance structures will be explored (ie, first-order autoregressive, compound symmetry).

$\text{Log (hSBA)} = \text{race} + \text{sex} + \text{geographic location (US; ex-US)} + \text{age at randomization} + \text{visit}$ .  
The intercept will be set as random effect.

Race categories other than White, Black, or Asian will be combined into a separate category termed "Other."

In addition to Type III analysis output, least-squares GMTs at each visit will be summarized for each strain.

These analyses will use the mITT population, using ½ LLOQ to impute the hSBA values below LLOQ for the primary strains only.

Similar to GMT, GLIMMIX will be utilized. The response variables are binary variables (composite response and 4-fold response) and a Logit link will be used. The model will be similar to the above. As 4 out of 5 endpoints (4-fold responses) will not have a response at Visit 1, the GLIMMIX model will use baseline hSBA titer as covariate and blood sampling time points at Visits 2, 3, and 4 as repeated dependent variables. The composite response

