analyses will be similar to the GMT analyses, with composite responses at all 4 visits modeled as dependent variables. This analysis will only be applied to the mITT population. The model-estimated response rates and the 95% CI will be summarized for each of the 5 coprimary endpoints at each applicable time point.

For the hSBA assay results, the following values will be set to missing: QNS (insufficient sera), indeterminate results, and not done. Subjects without blood draws (ie, dropout) will also have missing data for immunogenicity.

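### The GMT sensitivity model in SAP 5.3.1 gives each covariate one effect across all visits, including pre-vaccination Visit 1, so it can leave a substantial share of covariate-related dropout bias at Visit 4 uncorrected (minor)

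*SAP*

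**What the plan says.** SAP 5.3.1 bases the primary analysis on observed, determinate results without imputation, on the expectation that assay data are missing completely at random. If 10% or more of subjects in any stratum lack primary-strain hSBA data, a mixed model for repeated measures is fitted to Groups 2 and 4 in the mITT population, under a missing-at-random assumption.

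- **Fixed effects:** race, sex, geographic location, age at randomization and visit. No interaction is listed.
- **Covariance:** "To account for the intrasubject correlation among the repeated measures, an unstructured covariance matrix will be used". If the model does not converge, "further covariance structures will be explored (ie, first-order autoregressive, compound symmetry"). In addition, "The intercept will be set as random effect".
- **Outcome visits:** the same section says the composite-response "analyses will be similar to the GMT analyses, with composite responses at all 4 visits modeled as dependent variables". Together with "In addition to Type III analysis output, least-squares GMTs at each visit will be summarized for each strain", this makes Visit 1 an outcome in the GMT model.
- **Values below LLOQ:** set to half the LLOQ.
- **4-fold response model:** here "the GLIMMIX model will use baseline hSBA titer as covariate", and only Visits 2, 3 and 4 are outcomes.

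Protocol section 3 states that all subjects are naive to MenB vaccine at enrollment. Neither document gives a titer SD, a between-visit correlation, a covariate effect or a dropout pattern, and neither states the covariate margins for the least-squares GMTs.

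**The concern.** The model is the planned check on whether observed-case GMTs survive missingness related to the listed covariates. To be that check, it must estimate how those covariates act on the Visit 4 titer. As written, it forces the effect of age, sex, race or region on a pre-vaccination titer to equal the effect one month after dose 2. In unvaccinated subjects, many of whose Visit 1 values may sit at one constant, there is no reason to expect that equality.

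If the covariate acts only after vaccination, the common effect lies between its zero effect at Visit 1 and its true effect at Visit 4. Dropouts' Visit 4 titers are then predicted with too little adjustment. The model's GMT can stay close to the observed-case GMT even when the listed covariates drive dropout, and agreement between the two would reassure more than it should.

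**Working it through.** **The plan's own figures.** The SAP gives no number for this model. The nearby sample-size figures reproduce (900/0.85 = 1059 against about 1060; overall power 95.19% against 95.2%) but do not involve it.

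**Assumed inputs** (none is in the documents):
- One binary covariate split 50/50, with Visit 4 GMT ratio 0.6, so the log effect is ln 0.6 = -0.51. Its effect at Visit 1 is zero.
- Visit 4 missing in 25% of the low-titer group and 5% of the other, 15% overall.
- Log-SD 0.9, 0.9 and 1.1 at Visits 2, 3 and 4; Visit 1 SD varied from 0.3 to 0.9.
- Correlation 0.3 between Visit 1 and later visits, 0.6 among later visits.

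**Step 1: observed-case bias.** The low-titer share among those observed is 0.75/(0.75 + 0.95) = 0.441 instead of 0.5. Bias = -0.51 x (0.441 - 0.5) = +0.030 on the log scale, so the GMT is about 3% too high.

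**Step 2: what sets the common effect.** With complete data, generalized least squares weights the visit-specific effects by w = (row sums of the inverse covariance matrix) / (their total).

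| Visit 1 log-SD | Weight on Visit 1 |
|---|---|
| 0.3 | 99% |
| 0.4 | 92% |
| 0.6 | 71% |
| 0.9 | 42% |

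Under compound symmetry (equal variances and correlations) the weight is 1/4 = 25%. At Visit 1 SD 0.3 to 0.4 the fitted slope lies between -0.04 and 0.00, against a true Visit 4 effect of -0.51.

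**Step 3: share of the Visit 4 bias removed.** Share = 1 - (bias of the model's Visit 4 mean at the population covariate mix) / (observed-case bias). This is the large-sample maximum-likelihood limit with an unstructured matrix, over Visit 1 SD 0.3 to 0.9 and with the effect at Visits 2-3 either half the Visit 4 effect or equal to it.

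| When dropouts leave | Model as written | With visit-by-covariate terms |
|---|---|---|
| Before Visit 2 | 0-35% | 100% |
| Spread over the intervals | 29-70% | 100% |
| After Visit 3 | 45-46% (half effect) or 88-90% (equal effect) | 100% |

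The share rises with later dropout because titers observed at Visits 2 and 3 carry the covariate's effect to Visit 4 through the covariance matrix. If the effect is the same at all four visits, the model as written removes 100%.

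**Step 4: a second set of assumptions.** Sixty settings used Visit 1 SD 0.3-1.2, later SD 1.2, correlations 0.1-0.4 with Visit 1 and 0.4-0.8 afterwards, 8% against 30% missing, and log effects 0, 0.40, 0.35 and 0.6 at Visits 1 to 4.
- Model as written, unstructured: 0-58% removed, median 44%, below half in 72% of settings.
- Compound-symmetry fallback: 19-48%.
- Visit 1 effect set to a quarter of the Visit 4 effect: 25-60%, median 52%.
- Visit 1 dropped as an outcome, common effects kept: 64-75% where this was examined.
- Visit-by-covariate terms: 100%.

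In a further case with log effects 0.8, 0.7 and 0.6 at Visits 2-4 and none at Visit 1, up to 96% was removed. With the documents' region mix (270/1590 = 17% ex-US), 15% missing overall and 20-40% missing ex-US, the observed-case bias itself was 0.6-3%.

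**Step 5: margins.** Default least-squares means weight US and ex-US equally. If the model estimated a regional GMT ratio of 1.3 (assumed), this would shift the GMT by 1.3^(0.5 - 0.17) = 1.09, or 9%.

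**The case against.** **Not a general failure.** An unstructured repeated-measures model corrects partly through Visits 2 and 3, and the share removed ranges from 0% to 100% with the assumptions. This stands. A reader might infer that Visit 1 fixes the covariate effects and that most of the bias always remains. The documents do not support that: it needs a Visit 1 variance well below the later ones, which they never report, and little information from Visits 2-3. The weight on Visit 1 also falls under the compound-symmetry fallback. That fallback is a realistic possibility, because a random intercept on top of an unstructured matrix is redundant. It does not rescue the model, though (19-48% removed).

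**Small and without a decision rule.** With SD 1.1 and 850 observed subjects, the 95% half-width of a GMT is exp(1.96 x 1.1/sqrt(850)) - 1 = 7.7%, more than twice the whole 3% bias. The 15% missing rate may also be high: the protocol's 85% evaluable figure excludes subjects with out-of-window draws or protocol deviations, many of whom still have titers and stay in the mITT population. The model is conditional, and GMTs are secondary and descriptive. All of this stands and limits the severity.

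**The 4-fold model as template.** A reader might infer that it already avoids the problem. It does not take Visit 1 as an outcome, but it is described as similar to the GMT model, so it still has one covariate effect across Visits 2-4. Dropping Visit 1 alone removed only 64-75% of the GMT bias.

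**Timing.** SAP 3.5.2.2 speaks of Stage 1 reporting as already done, so a change now comes after unblinding. This bears on how the analysis is labelled, not on whether the model is well specified.

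**Conclusion.** The concern holds as a minor specification weakness. The GMT model has no visit-by-covariate terms and takes Visit 1 as an outcome, so it is mis-specified for any covariate that acts on vaccine response but not on the baseline titer. In that case it can leave a substantial share, often half or more, of covariate-related dropout bias at Visit 4. The exact share cannot be fixed from the documents, because Visit 1 variance, correlations, dropout timing and effects at Visits 2-3 are all unstated.

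It would be wrong to infer that the primary conclusion is at risk. The five coprimary endpoints are tested on observed binary results with Clopper-Pearson limits, and no decision rule uses this model. What is weakened is the reassurance that agreement between the model-based and observed-case GMTs could offer.

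**What to change.** In SAP 5.3.1, add visit-by-race, visit-by-sex, visit-by-region and visit-by-age terms to the GMT model, and state that least-squares GMTs are reported at the observed mITT covariate margins. Do not rely on removing Visit 1 as an outcome while keeping common effects.

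The cost is a few degrees of freedom with roughly 1,000 subjects, some SAP wording and a rerun. No new data are needed. Because Stage 1 has been unblinded and reported, label the result a post hoc supportive analysis and show it beside the model as written.

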### **5.3.2. Safety Data**

Standard algorithms on handling missing AE dates and missing AE severity will be applied as described in the safety rulebook summary.

#### **5.3.2.1. Reactogenicity Data**

For derived variables based on reactogenicity data, if any day of the 7-day e-diary is available, the “any day (Days 1 to 7)” data will be considered as nonmissing. Subjects are excluded from the analysis if they do not receive the particular dose or the safety data are missing on all days within the interval.

The reactogenicity data are collected in the e-diary, which does not allow subjects to skip the question. Therefore, for a specific day, as long as the e-diary data are transferred for that day, all of the reactogenicity data for the subject on that day are nonmissing. The e-diary transmission and completion status will be summarized per [Section 6.6.3](#). The e-diary completion summary will provide the missing data information on the reactogenicity data.

Based on data from available studies, the missing data on reactogenicity are minimal, which is consistent with Li et al (2011). No sensitivity analysis is planned for reactogenicity data.

## **6. ANALYSES AND SUMMARIES**

For immunogenicity analysis, Groups 2 and 4 (bivalent rLP2086+MenACWY-CRM) and Groups 1 and 3 (MenABCWY) will be combined for MenB analysis, while MenA/C/W/Y analysis will be reported and analyzed per individual group separately.

### **6.1. Primary Endpoints**

The primary immunogenicity and primary safety endpoints will be summarized for Stage 1 of the study. Report summaries will combine subjects in Groups 2 and 4. Subject data listings may also be produced.

### 6.1.1. Primary Immunogenicity Endpoints

The 5 coprimary endpoints will be descriptively summarized by reporting the number of subjects with valid and determinate primary MenB assay titers at baseline and 1 month post-Vaccination 2. The number of subjects who have a  $\geq 4$ -fold rise from baseline will be displayed by the 4 MenB primary strains along with the associated percentage and 2-sided 95% CIs. The composite response will also be similarly displayed (see [Table 17](#)).

The 2-sided 95% CIs for the proportions of subjects meeting each of the 5 primary endpoints will be calculated using the Clopper-Pearson method described in [Section 5.2.1.1](#). The analysis will be performed on Groups 2 and 4 combined.

The primary analysis and hypothesis testing will be conducted on the Stage 1 evaluable immunogenicity population. If the LCI of subjects in the Stage 1 evaluable population exceeds the corresponding target LCI for each strain and the composite ([Table 15](#)), the null hypothesis will be rejected.

The evaluation for the 5 coprimary endpoints will be performed for the US evaluable subjects separately as well as on all evaluable subjects.

A similar analysis will be performed on the Stage 1 mITT population.

**Table 17. Analysis for Primary Immunogenicity Endpoints**

Stage of Study	Objective	Randomized Groups	Analysis Time Point	Analysis Population(s)	Variant/Strain	Analysis Endpoint
Stage 1	MenB immune response after 2 doses of bivalent rLP2086	2+4	Visits 1 and 4 (baseline, post-Vaccination 2 blood draw)	Stage 1 evaluable immunogenicity – US subjects only, Stage 1 evaluable immunogenicity, Stage 1 mITT, Stage 1 mITT – US subjects only	PMB80(A22) PMB2001(A56) PMB2948(B24) PMB2707(B44)	Composite response (proportion of subjects achieving an hSBA titer $\geq$ LLOQ for all 4 strains) Subjects achieving at least a 4-fold increase in hSBA titer from baseline for each of the 4 strains

Abbreviations: hSBA = serum bactericidal assay using human complement; LLOQ = lower limit of quantitation; MenB = *Neisseria meningitidis* serogroup B; mITT = modified intent-to-treat.

### **6.1.2. Primary Safety Endpoints**

Safety endpoint data will be summarized according to vaccine received. The safety population at each corresponding AE analysis interval ([Table 6](#), [Table 7](#), and [Table 8](#)) will be used for the analysis of each AE endpoint. The primary safety endpoints will be displayed for the Stage 1 safety populations and Groups 2 and 4 combined. The primary safety endpoints for booster vaccination will be displayed for the booster safety population for Groups 1 through 4.

#### **6.1.2.1. Local Reactions and Systemic Events**

The derived variables for the presence of each local reaction, each systemic event, any local reaction, and any systemic event occurring within 7 days following each vaccination will be summarized.

The presence and maximum severity of each reaction/event and any reaction/event within 7 days (over all Days 1 to 7) after each vaccination and any vaccination will be summarized through proportions of subjects, percentages, and associated 95% Clopper-Pearson CIs.

For each local reaction and systemic event, the maximum duration of each reaction/event will be descriptively summarized for each vaccination. Only subjects experiencing the reaction/event will be included in the analysis.

Use of antipyretic medication will also be displayed by the number of subjects and percentage who used antipyretic medication on each day and any day after each vaccination and any vaccination. Maximum duration of use will also be summarized by vaccination.

#### **6.1.2.2. Serious Adverse Events, Medically Attended Events, and Newly Diagnosed Chronic Medical Conditions**

The number and percentage of subjects experiencing at least 1 SAE/MAE/NDCMC and the number of events will be descriptively summarized according to the analysis intervals in [Table 6](#) with 95% exact CIs (Clopper-Pearson method) for the percentages (see [Section 5.2.1.1](#)).

Summaries will be displayed by system organ class (SOC) and preferred term (PT, coded with MedDRA) and reported in accordance with the Pfizer reporting standards. All displays will be sorted in alphabetical order within SOC and PT. Subjects reporting events with the same SOC or PT will only be counted once; however, all events reported will be included in the number of events.

#### **6.1.2.3. Adverse Events**

Adverse events will be summarized similarly to SAEs/MAEs/NDCMCs (Section 6.1.2.2) per the analysis interval described in [Table 6](#). Nonserious AEs are not required to be reported during the follow-up phase. However, if nonserious AEs during the follow-up phase were recorded in the database (excluding MAEs and nonserious NDCMCs), these data will be listed in the overall AE listing.

Note that for the analysis interval of vaccination phase, the AEs will be summarized by SOC and PT with number and percentage of subjects reporting each event and number of events. Subjects reporting events with the same SOC or PT will only be counted once, but all events reported will be included in the number of events. Percentages and 95% CIs will also be provided.

#### **6.1.2.4. Immediate Adverse Events**

The number and percentage of subjects reporting AEs occurring within the 30-minute observation period immediately after vaccination will be summarized according to the analysis intervals defined in [Table 7](#). These summaries will include 95% Clopper-Pearson's CIs.

#### **6.1.2.5. School and Work Days Missed**

The total number of days a subject missed school and/or work will be descriptively summarized for subjects in Stage 1 and in Groups 2 and 4 combined. Similar descriptive summaries will be presented for the subjects missing school and/or work after booster vaccination in Groups 1 through 4.

### **6.2. Secondary Endpoints**

#### **6.2.1. Secondary Immunogenicity Endpoints**

Stage 1 secondary immunogenicity endpoint data will be summarized according to randomized vaccine for subjects included in the Stage 1 mITT population. The Stage 1 MenB strain endpoints will also be summarized on the Stage 1 evaluable immunogenicity population. Vaccine misallocations concerning vaccine history and ACWY strata as described in [Section 4.5](#) will apply.

Persistence will be summarized for subjects included in the Stage 2 mITT populations. Booster vaccination will be summarized for subjects included in the booster evaluable immunogenicity population.

For immunogenicity endpoints relating to MenACWY strains, subjects in the experienced ACWY stratum who received monovalent C vaccine will only contribute to the serogroup C analyses, while subjects who received quadrivalent vaccine will contribute to the full serogroup analyses.

##### **6.2.1.1. Bivalent rLP2086 Immune Response Secondary Objectives**

Immune response data will be combined for vaccine Groups 2 and 4 for the Stage 1 analyses for secondary endpoints. Immune response data will be reported for subjects in Groups 2 and 4 combined for the booster analyses for secondary endpoints.

The Stage 1 analysis for secondary endpoints will be descriptively summarized on the 4 MenB primary strains as well as the 10 MenB secondary strains. Analyses of hSBA titers obtained at the analysis time points detailed in [Table 18](#) will be summarized accordingly.

The number and percentage of subjects meeting the following analysis endpoint criteria outlined in [Table 18](#) will be summarized. Primary and secondary strain LLOQs are defined in [Table 16](#). The 2-sided 95% CIs for the proportions of subjects meeting each of the analysis endpoints will be calculated using the Clopper-Pearson method described in [Section 5.2.1.1](#).

The GMTs at each analysis time point and for each strain as outlined below will also be summarized. See [Section 5.2.2.1](#) for calculation of GMTs.

A listing of assay data will be provided by vaccine group, analysis time point, and MenB strain.

**Table 18. Analysis for Bivalent rLP2086 Immune Response Secondary Objectives**

Stage of Study	Objective	Randomized Groups	Analysis Time Point	Analysis Population(s)	Strains	Analysis Endpoint
Stage 1	MenB response after 2 doses of bivalent rLP2086	2+4	Visits 1 and 4 (baseline and post-Vaccination 2 blood draw)	Stage 1 evaluable immunogenicity, Stage 1 mITT	PMB80(A22) PMB2001(A56) PMB2948(B24) PMB2707(B44)	Subjects with hSBA titer $\geq$ LLOQ for each strain Subjects with hSBA titer $\geq$ 1:4, $\geq$ 1:8, $\geq$ 1:16, $\geq$ 1:32, $\geq$ 1:64, and $\geq$ 1:128 for each strain hSBA GMTs for each strain
			Visits 1 and 4 (baseline and post-Vaccination 2 blood draw)		PMB3175(A29) PMB3010(A06) PMB824(A12) PMB3040(A07) PMB1672(A15) PMB1989(A19) PMB648(B16) PMB866(B09) PMB1256(B03) PMB431(B15)	Subjects with hSBA titer $\geq$ LLOQ for each strain Subjects with hSBA titer $\geq$ 1:4, $\geq$ 1:8, $\geq$ 1:16, $\geq$ 1:32, $\geq$ 1:64, and $\geq$ 1:128 for each strain hSBA GMTs for each strain
Booster	MenB response after bivalent rLP2086 booster dose	2+4	Visits 4, 10, and 11 (post-Vaccination 2, pre-booster vaccination, postbooster blood draw)	Booster evaluable immunogenicity	PMB80(A22) PMB2001(A56) PMB2948(B24) PMB2707(B44)	Subjects with hSBA titer $\geq$ LLOQ for each strain

Abbreviations: GMT = geometric mean titer; hSBA = serum bactericidal assay using human complement; LLOQ = lower limit of quantitation; MenB = *Neisseria meningitidis* serogroup B.

### 6.2.1.2. MenABCWY Immune Response Secondary Objectives

MenABCWY immune response data for hSBA-MenA, hSBA-MenB, hSBA-MenC, hSBA-MenW, and hSBA-MenY titers will be descriptively summarized. Descriptive comparisons between vaccine groups will also be displayed for the Stage 1 data. For MenB strain response, as all subjects are naïve to MenB vaccine at entry, comparisons will be between the combined strata vaccine groups (Groups 2+4 versus Groups 1+3). For ACWY strain response, comparisons will be between vaccine groups within ACWY strata (Groups 1 versus 2 and Groups 3 versus 4).

Experienced ACWY strata subjects who only received prior vaccination with monovalent C vaccine will be excluded from immune response assessments for strains MenA/W/Y and will only be included in MenC assessments.

The empirical reverse cumulative distribution curves (RCDCs) will be presented graphically using a step function for each of the 4 primary MenB strains and the hSBA-MenA/C/W/Y strains at Visits 1, 2, and 4. Additional RCDC curves may be presented for persistence and booster analysis time points for the 4 primary MenB strains and the hSBA-MenA/C/W/Y strains.

Immune response in the 4 primary MenB strains and in the hSBA-MenA/C/W/Y strains on blood draw data obtained prior to receiving the booster vaccination will be summarized.

Descriptive analyses on each of the hSBA titers at various analysis endpoints and for the analysis timelines as defined in [Table 19](#) will be similarly summarized as described in [Section 6.2.1.1](#).

